**15.6.11 The exploratory endpoints to be analyzed are:**

- To evaluate the efficacy of P2B001 0.6/0.75 mg compared to its individual components in the following endpoints:
  - Change from baseline to Week 12/Treatment Termination visit in each of the 8 PDQ39 subscales scores.
  - Change from baseline to Week 12/Treatment Termination visit in Health-Related Quality of Life (HRQOL) SF-12v2 questionnaire.

- Clinical Global Impression of Improvement (CGI-I) at Week 12/Treatment Termination visit.
- To evaluate the superiority of P2B001 0.6/0.75 mg over Pramipexole ER with respect to the following outcome measures:
  - Proportion (%) of patients with ESS score >10 at Week 12/Treatment Termination.
  - Proportion (%) of patients with ESS Score  $\leq$ 10 at baseline and ESS score >10 at Week 12/Treatment Termination.
  - 3-Months rate of total number of adverse events.
  - Change from baseline to Week 12/Treatment Termination in the differences in systolic and diastolic blood pressure measured during supine and standing positions.
  - Proportion (%) of patients with both symptomatic/non-symptomatic Orthostatic Hypotension.
  - 3-Months rate of total number of both symptomatic/non-symptomatic Orthostatic Hypotension.
  - Proportion (%) of patients with symptomatic Orthostatic Hypotension.
  - 3-Months rate of total number of symptomatic Orthostatic Hypotension.
  - Proportion (%) of patients with daytime sleepiness/drowsiness related AE's.
  - Proportion (%) of patients with gastrointestinal (GI) adverse events
  - Proportion (%) of patients presenting neurological adverse events
  - Change from baseline to Week 12/Treatment Termination visit in the Orthostatic Hypotension Symptoms Assessment (OHSA) question 1.
- To descriptively evaluate the comparability of P2B001 0.6/0.75 mg with reference to the calibration arm (Pramipexole ER) in total UPDRS score (defined as sum of parts II and III, scores (0-160)).

## 15.7 Safety Assessments

All safety assessments will use the Safety Analysis Set (ST) which includes all randomized subjects who were administered at least one study dose, according to the treatment actually received. The ST analysis set will serve as the principal analysis set for safety assessment. Safety analyses will exclude measurements taken 30 days after study treatment discontinuation as well as adverse events initiated 30 days after study treatment discontinuation.

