### **9.2 Study Procedures**

#### **9.2.1 Detailed Study Plan**

A detailed Schedule of Activities is provided in Appendix I.

The study includes 7 visits. The first visit will allow screening of potential subjects that will participate in the study. This period of time between the screening visit and enrollment of a subject to the study is named the screening phase. The treatment phase is when subjects are receiving treatment with the study drugs. During the treatment phase, subjects' condition will be evaluated every 3-5 weeks (visits 2-6). The first 6 weeks of the treatment period will include a titration of the Pramipexole ER dose or its placebo to optimal dose (titration phase). One capsule a day of P2B001/PPX 0.6/RAS 0.75/Placebo will be taken at this time without any need for titration. This will be followed by a maintenance phase ending at the end of week 12. The safety follow up phase will start after week 12 which will include a week (week 13) of no treatment of the P2B001 or its components and a down-titration of pramipexole ER or its placebo. Week 14 will include no treatment at all. The end of the study drug treatment and a follow up safety visit will be performed at the end of week 14 (visit 7).

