#### ***9.2.11.1 Follow-up visits of subjects that have terminated the study treatment early***

ETT subjects will be requested to continue with all study visits and activities as planned, for follow up, without taking any study medication. During these visits, all questionnaires and assessments will continue as planned for follow up. Accountability will be omitted since study drug was returned at the ETT visit.

Subjects may take rescue therapy during the follow-up visits; this will be documented in the concomitant medication list.

ETT subjects that decided later to stop their participation in the study will be requested to undergo a study termination visit. **All activities listed in the treatment termination (visit 6) and safety visits (visit 7) will be performed at this visit.**

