### 15.7.1 Adverse Events

Adverse events will be recorded from the time a subject has signed the Informed Consent Form until the end of subject's study participation, including up to Week 14 Follow-Up visit, regardless of study IP administration.

The MedDRA dictionary will be used to standardize the terms used by the Investigator to describe the Adverse Events (AEs).

The following will be incorporated into the analysis of adverse events:

- As analysis of AEs can incorporate only coded AEs, it is mandatory that at the time of database lock all AEs will be coded.
- Adverse events analyses will include only the Treatment Emergent Adverse Events (TEAEs), namely, those events which started at the time of first study IP administration or afterwards. AEs lacking start day or AEs recorded on day of first study IP lacking start time will be considered as TEAE.

The following analyses are pre-planned for adverse events:

- The incidence (no. of patients) and frequency (no. of events) of most frequent TEAEs (>5% of subjects in at least one study arm) by Preferred Term (PT).
- The incidence (no. of patients) and frequency (no. of events) of TEAEs broken down by System Organ Class (SOC) and PT.
- The incidence (no. of patients) and frequency (no. of events) of TEAEs by SOC and PT in Subjects Early Discontinued from Study/Treatment.
- The incidence (no. of patients) and frequency (no. of events) of serious TEAEs by SOC and PT
- The incidence (no. of patients) and frequency (no. of events) of TEAEs when broken down by severity.
- The incidence (no. of patients) and frequency (no. of events) of TEAEs broken down by relationship to study IP.
- The incidence (no. of patients) and frequency (no. of events) of TEAEs when broken down by action taken with study IP.
- The incidence (no. of patients) and frequency (no. of events) of TEAEs when broken down by event outcome.
- Adverse Events dictionary used to code Investigator's verbatim terms will be provided.
- Individual subject listings of all SAEs, treatment emergent SAEs, TEAEs and non-TEAEs.

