#### **15.11 Exploratory Safety Endpoint**

Exploratory comparison between P2B001 0.6/0.75 mg and Pramipexole ER at Week 12/Treatment Termination will be performed in the following safety endpoints:

- Change from baseline to Week 12/Treatment Termination in the ESS score > 10.
- Adverse event frequency
- Change from baseline to Week 12/Treatment Termination in the differences in systolic and diastolic blood pressure measured during supine and standing positions.
- Comparison of percentage of patients presenting with sleepiness/drowsiness related AE’s.
- Comparison of percentage of patients presenting with gastrointestinal (GI) adverse events.
- Comparison of percentage of patients presenting with neurological adverse events.
- Change from baseline to Week 12/Treatment Termination visit in the Orthostatic Hypotension Symptoms Assessment (OHSA) question 1.

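### Adverse event comparisons with pramipexole ER, counted as section 15.7 says, include a week in which only the ER arm is on active drug, while section 15.11 places them at Week 12

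*Protocol*

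**What the plan says.** - **General safety window.** Protocol section 15.7 states: "Safety analyses will exclude measurements taken 30 days after study treatment discontinuation as well as adverse events initiated 30 days after study treatment discontinuation". It does not say whether discontinuation means the last capsule or the last tablet.
- **Which events are analysed.** Section 15.7.1 limits AE analyses to treatment-emergent events, meaning "those events which started at the time of first study IP administration or afterwards". That definition has no end date. Recording runs "until the end of subject's study participation, including up to Week 14 Follow-Up visit, regardless of study IP administration".
- **Week 13.** Section 9.2.1 describes this week as "no treatment of the P2B001 or its components and a down-titration of pramipexole ER or its placebo". Section 6.1 confirms that no capsules are taken during the 7-day taper. Week 14 is free of treatment in every arm.
- **Early stoppers.** Under section 7.5, capsules can stop at once but tablets are tapered. Section 9.2.11.1 adds: "Subjects may take rescue therapy during the follow-up visits".
- **The comparison.** Section 15.6.11 lists endpoints on which superiority over pramipexole ER is to be evaluated. They include "3-Months rate of total number of adverse events" and the proportions with sleepiness, gastrointestinal and neurological AEs. It gives neither a counting window nor a person-time denominator.
- **A different time point.** Section 15.11 says: "Exploratory comparison between P2B001 0.6/0.75 mg and Pramipexole ER at Week 12/Treatment Termination will be performed", and AE frequency is on its list. For analyses with significance testing, section 15 defines Week 12/Treatment Termination as the last visit at which the subject was on study drug.

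**The concern.** Section 4 states the intention to show safety benefits of P2B001 relative to pramipexole ER, and these AE contrasts are the material for that claim. Under the general rule, the count runs through a week in which one arm takes active drug and the other takes none. Early stoppers add time off drug, possibly on another antiparkinsonian treatment. Section 15.11 implies a count ending when treatment ends. The two rules can give different answers from the same data, and the documents do not say which applies. At stake is whether a small difference in AE frequency reflects the drugs or the calendar.

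**Working it through.** The plan gives no expected AE rate or power for these comparisons, so there is no figure to reproduce. The check is person-time arithmetic from the schedule.

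**Inputs.** Treatment lasts 12 weeks = 84 days; the tablet taper lasts 7 days; observation ends at Week 14 = 98 days (sections 6.1 and 9.2.1, Appendix I). Planned arm sizes are 150 for P2B001 and 75 for ER (section 15).

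**Active time, completers.**
- P2B001: 84/98 = 85.7%.
- ER: (84 + 7)/98 = 91/98 = 92.9%.

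**Event ratio over a common denominator.** Assume equal on-drug risk in both arms and off-drug risk equal to a fraction b of it (b is my assumption). The P2B001/ER ratio is (84 + 14b)/(91 + 7b) = (12 + 2b)/(13 + b).

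| b | Taper week at full on-drug risk | Taper week carrying half the excess risk |
|---|---|---|
| 0 | 12/13 = 0.923 | 12/12.5 = 0.960 |
| 0.25 | 12.5/13.25 = 0.943 | not shown |
| 0.5 | 13/13.5 = 0.963 | 13/13.25 = 0.981 |
| 1 | 14/14 = 1.000 | 1.000 |

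**Proportions.** A subject counts once, so the ratio lies closer to 1. As an illustration, take the 20.4% with nausea on P2B001 0.6/0.75 in the phase 2b table (section 3.4) as a 12-week risk with constant hazard and no off-drug risk. Thirteen active weeks would give 1 − 0.796^(13/12) = 21.9%. That is a ratio of 0.93 and a difference of 1.5 percentage points.

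**Each arm's own active days as denominator, events still counted to Week 14.** The ratio becomes [(84 + 14b)/84] / [(91 + 7b)/91]:
- b = 0: 1.00.
- b = 0.5: 1.083/1.038 = 1.04.
- b = 1: 1.167/1.077 = 1.08.

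The artefact now runs against P2B001.

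**Early stoppers.** For a P2B001 subject stopping on day s with a full 30-day tail, the share of counted time off drug or on rescue is 30/(s + 30). It is 30/51 = 59% at day 21, 30/65 = 46% at day 35 and 30/86 = 35% at day 56.

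**Effect on a nominal 5% test.** I used a Wald test on the log rate ratio with SE = √[(1/μ + k)(1/150 + 1/75)], assuming a mean μ of 1 to 3 AEs per subject and dispersion k of 0 to 1. A pure 13/12 = 1.083 artefact (ER over P2B001) gives a false-positive rate of 6.8% to 16.4%. A 1.038 artefact gives 5.4% to 7.4%.

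**Counting to the last capsule.** Completers contribute 84 days in each arm, and the ratio is 84/84 = 1.00.

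**The case against.** The strongest reply is that the link is inferred. The three-month rates sit in section 15.6.11 and are assigned to the ITT set. The 30-day rule sits in section 15.7 and is tied to the Safety Analysis Set. Section 15.11, the text closest to the comparison, already names Week 12/Treatment Termination. Detailed exploratory methods are deferred to the SAP, which overrides the protocol (section 15.13). Only the addendum to SAP Version 2.0 is available, and it deals with the mITT set. This stands as a limit: the protocol text is unreconciled, but SAP Version 2.0 may already settle the matter.

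Other replies also hold in part:
- The taper belongs to the ER regimen, so charging taper events to ER is a legitimate comparison of whole strategies. That argues for keeping the full window as a second analysis, but not for leaving the window unstated.
- Zero off-drug risk in week 13 is doubtful, because rasagiline is an irreversible inhibitor (section 3.1) and the ER dose falls during the taper. Both points shrink the artefact.
- Appendix I schedules no clinic visit in week 13, which limits detection of non-symptomatic orthostatic hypotension in that week.

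A reader might go further and infer that every subject is counted for 30 days after stopping. For completers, recording ends at Week 14: 14 days after the last capsule and about 7 after the last tablet. A reader might also infer that rescue-treated time favours P2B001. Rescue is open to all arms and biases the contrast only if early stopping or rescue differs by arm.

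**Conclusion.** The point holds in a limited form. Followed as written, sections 15.7 and 15.7.1 compare 84 with 91 active days among completers, and they conflict with the time point in section 15.11. For proportions and common-denominator rates, the effect is modest and tends to favour P2B001. The event ratio is at worst 0.92, about 0.96 with off-drug risk at half the on-drug risk, and nearer 1 if the taper week carries less risk. These figures assume equal on-drug risk in the two arms and constant risk over time.

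It does not follow that the three-month rates are biased towards P2B001. Their denominator is not given, and dividing by active days can reverse the direction. Nor is 12/13 an expected value: it requires a full-risk taper week and no events off drug.

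The endpoints are exploratory and not multiplicity-controlled. Section 15 calls comparisons with ER other than the Epworth Sleepiness Scale descriptive, whereas the exploratory text closing section 15.6.10.5 allows nominal 5% tests. The false-positive figures matter only if such tests are run. Primary and gatekept conclusions are unaffected.

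**What to change.** First check whether SAP Version 2.0 already sets the window and denominator. If it does not, before unblinding:

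- State in sections 15.6.11 and 15.11 that AE comparisons with pramipexole ER count events with onset from first dose to the last capsule (Week 12 or early treatment termination), with rates over that same exposure time.
- Say in section 15.7 whether discontinuation means the last capsule or the last tablet.
- Report events from the taper, the follow-up week and time after early termination, including rescue-treated time, separately and descriptively.
- Repeat the comparison over the full window as a sensitivity analysis, because differential early stopping can affect the truncated proportions.
- Keep the 30-day window for the general safety tables.

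The cost is some wording and a date cut-off in the AE programs. No new data are needed. The downside is slightly fewer events in the main comparison.

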### 15.7.1 Adverse Events

Adverse events will be recorded from the time a subject has signed the Informed Consent Form until the end of subject's study participation, including up to Week 14 Follow-Up visit, regardless of study IP administration.

The MedDRA dictionary will be used to standardize the terms used by the Investigator to describe the Adverse Events (AEs).

The following will be incorporated into the analysis of adverse events:

- As analysis of AEs can incorporate only coded AEs, it is mandatory that at the time of database lock all AEs will be coded.
- Adverse events analyses will include only the Treatment Emergent Adverse Events (TEAEs), namely, those events which started at the time of first study IP administration or afterwards. AEs lacking start day or AEs recorded on day of first study IP lacking start time will be considered as TEAE.

The following analyses are pre-planned for adverse events:

- The incidence (no. of patients) and frequency (no. of events) of most frequent TEAEs (>5% of subjects in at least one study arm) by Preferred Term (PT).
- The incidence (no. of patients) and frequency (no. of events) of TEAEs broken down by System Organ Class (SOC) and PT.
- The incidence (no. of patients) and frequency (no. of events) of TEAEs by SOC and PT in Subjects Early Discontinued from Study/Treatment.
- The incidence (no. of patients) and frequency (no. of events) of serious TEAEs by SOC and PT
- The incidence (no. of patients) and frequency (no. of events) of TEAEs when broken down by severity.
- The incidence (no. of patients) and frequency (no. of events) of TEAEs broken down by relationship to study IP.
- The incidence (no. of patients) and frequency (no. of events) of TEAEs when broken down by action taken with study IP.
- The incidence (no. of patients) and frequency (no. of events) of TEAEs when broken down by event outcome.
- Adverse Events dictionary used to code Investigator's verbatim terms will be provided.
- Individual subject listings of all SAEs, treatment emergent SAEs, TEAEs and non-TEAEs.

### **15.7.2 Laboratory Tests**

Analyses of safety central laboratory data will be performed in the following manner:

- The more detailed SAP to be developed while the study is ongoing and prior to locking the database and unblinding will provide quantitative criteria used to define the potentially clinically significant (PCS) abnormal laboratory values. Measurements to be used in the analysis are those taken only after the initiation of the 1st study IP administration. The incidence tables of PCS lab values as well as the individual subject listing will be provided. Please note that the denominator to be used for calculating percentages is the number of subjects with at least one measurement post initiation of the 1st study IP administration.

- Quantitative laboratory measurements will be categorized with reference to the normal ranges as Low, Normal or High. The incidence (no. of subjects) of abnormal values at any time post initiation of the 1st study IP administration, calculated for subjects with normal values at baseline will be provided. Analysis will include, per tested parameter, those subjects with normal baseline and at least one post-treatment measurement. Summary table will display the number and relative percentage of subjects with at least one abnormal value (above upper or below the lower normal range) at any time post initiation of the 1st study IP administration.
- Quantitative laboratory measurements will be categorized with reference to the normal ranges as Low, Normal or High. Shift analysis of the categorical change from baseline to each scheduled visit and to the last observed value will be provided. In case of sporadic repeated measurement within a visit, the last measurement per visit will be used to represent subject's value in the analysis.

Box-Plots of measurements done and figures of mean values  $\pm$  SEs as well as descriptive statistics for all laboratory quantitative parameters and changes from baseline will be provided by scheduled visits and treatment groups. In case of sporadic repeated measurement within a visit, the last measurement per visit will be used to represent subject's value in the analysis.

### **15.7.3 Vital Signs**

Analyses of vital signs will be performed in the following manner:

- The more detailed SAP to be developed while the study is ongoing and prior to locking the database and unblinding will provide quantitative criteria used to define the potentially clinically significant (PCS) abnormal values. Measurements to be used in the analysis are those taken immediately following the first administration of the study IP and onwards. The incidence tables of PCS values as well as the individual subject listing will be provided. The denominator to be used for calculating percentages is the number of subjects with at least one observation post 1st study IP administration.
- Box-Plots of measurements done, figures of mean values  $\pm$ SEs as well as descriptive statistics for all parameters and changes from baseline (derived) will be provided by scheduled visits and treatment groups. Please note that the last measurement per visit will be used to represent subject's value in the analysis in case of sporadic repeated measurement within a visit.

### **15.8 ECG**

The incidence of abnormal ECG findings will be presented by treatment group. Shift analysis from baseline will be provided as well.

### **15.9 Columbia Suicide Severity Rating Scale (CSSRS)**

The Columbia Suicide Severity Rating Scale Screening/Baseline Version (CSSRS-BL) will be taken at screening. The Columbia Suicide Severity Rating Scale Since Last Visit (CSSRS-SLV) was to be taken at baseline and in all subsequent study visits.

Any positive answer to its behavior subcomponents at screening or baseline will identify a subject as with “Suicidal Behavior at Baseline”. Similarly, any positive answer to it’s the ideation subcomponents at any of these two visits will identify a subject as with “Suicidal Ideation at Baseline”. A subject identified with either “Suicidal Behavior at Baseline” or with “Suicidal Ideation at Baseline” was also classified as with “Suicidal Behavior or Ideation at Baseline”. Similarly, any positive answer to its behavior subcomponents in any of the post-dosing visits will identify a subject as with “Suicidal Behavior Post Dosing”. Similarly, any positive answer to it’s the ideation subcomponents in any of the post-randomization visits will identify a subject as with “Suicidal Ideation Post Dosing”. A subject identified with either “Suicidal Behavior Post Dosing” or with “Suicidal Ideation Post Dosing” was also classified as with “Suicidal Behavior or Ideation Post Dosing”.

The distribution of the number of subjects by these classifications post-dosing as well as shift analysis from baseline will be displayed. In addition, for the CSSRS-SLV, listing of Post First Study Dose CSSRS (Ideation) Grade 4 and 5 / Suicidal Behavior will be provided.

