16. Any relevant medical, surgical, or psychiatric condition, laboratory value, or concomitant medication which, in the opinion of the Investigator, makes the subject unsuitable for study entry or potentially unable to complete all aspects of the study.
17. Subject has severe or moderate renal impairment (creatinine clearance <50 mL/min) or on dialysis.
18. Subject has moderate (Child-Pugh categorization B, score 7-9) or severe (Child-Pugh categorization C, score 10-15) hepatic impairment ( Lucey MR, 1997).

19. Subject has a lifetime history of suicide attempt (including an active attempt, interrupted attempt or aborted attempt), or has suicidal ideation in the past 6 months as indicated by a positive response ('Yes') to either Question 4 or Question 5 of the Columbia-Suicide Severity Rating Scale (CSSRS) at Screening.
20. Subject has known hypersensitivity or intolerance to pramipexole or rasagiline or to any components or excipients of the test drug or placebo.
21. Subject who has a history of neuroleptic malignant syndrome.
22. Subject who is pregnant or breastfeeding.
23. Subject, who, for any reason, is judged by the Investigator or the EMC to be inappropriate for this study, including a subject who is unable to communicate or cooperate with the Investigator or who has/had a clinically significant illness or abnormal physical examination that may compromise safety of the subject during the trial or affect ability of the subject to adhere to study procedures.

A site will not be allowed to randomize subjects unless their diagnosis and suitability for the study has been confirmed and documented by both the Investigator and the EMC and they are deemed to be a satisfactory candidate by the EMC.

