### **8.3.9 Suicidality**

Columbia Suicide Severity Rating Scale (CSSRS, see Appendix VIII) will be used. Baseline / screening version of the CSSRS will be used at screening visit. This version assesses suicidality in a patient's lifetime and during the past six months. The Since Last Visit (SLV) version of the CSSRS will be used at all consequent visits. This version assesses suicidality since the patient's last visit. Efforts must be made to ensure that the same trained team member completes this questionnaire for each subject.

A subject with any suicidal ideation that answered YES to questions 4 or 5 in the CSSRS questionnaire will be referred to a mental health professional.

CSSRS-SLV will be used on the baseline visit and at end of weeks 3, 5, 8, 12/Treatment Termination visit and end of week 14 (visits 3, 4, 5, 6 and 7).

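### The baseline suicidal-ideation flag in Section 15.9 takes in lifetime history, so new low-grade ideation in a subject with only remote history is tabulated as yes-to-yes and not as new onset

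*Protocol*

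**What the plan says.** Section 15.9 of the protocol assigns the Screening/Baseline version of the CSSRS to the screening visit and the Since Last Visit version to the baseline visit and all later visits. A positive answer to "the ideation subcomponents at any of these two visits will identify a subject as with" suicidal ideation at baseline. Neither a recall window nor a grade is attached. The post-dosing ideation class is set in the same yes/no way from the later visits.

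Section 8.3.9 gives the recall periods. The screening version covers the patient's "lifetime and during the past six months". Of the version used at later visits it says: "This version assesses suicidality since the patient's last visit".

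Exclusion criterion 19 (Section 7.4) has two parts. One applies when the "Subject has a lifetime history of suicide attempt". The other applies when the subject "has suicidal ideation in the past 6 months as indicated by a positive response" to Question 4 or 5 at screening. Older ideation of any grade is not an exclusion.

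Section 15.9 plans these outputs: "The distribution of the number of subjects by these classifications post-dosing as well as shift analysis from baseline will be displayed". It adds that a "listing of Post First Study Dose CSSRS (Ideation) Grade 4 and 5 / Suicidal Behavior will be provided".

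**The concern.** A shift table separates ideation that was already present from ideation that appeared on study. That works only if the baseline state and the on-study state are measured over comparable periods. Here the baseline flag can be set by something that happened decades ago, while the post-dosing flag covers about 14 weeks (12 weeks of treatment and the follow-up visit two weeks later).

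A subject with remote ideation only, none in the past six months and none at the baseline visit, who then reports ideation on treatment, has new on-study ideation in any ordinary sense. Under the stated rule that subject cannot move from no to yes. Of the outputs named in Section 15.9, only the shift analysis is designed to separate new from pre-existing ideation, so the misclassification falls on the one display meant to show it.

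**Working it through.** No sample-size, power or alpha figure bears on this point, so there is no planned number to reproduce. The check is to apply the rule to every possible set of answers.

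**Inputs**
- Baseline rule: positive if any ideation answer at screening or baseline is positive (Section 15.9).
- Screening form: lifetime and past six months (Section 8.3.9).
- Baseline visit and later: Since Last Visit form (Sections 8.3.9 and 15.9).
- Eligibility: remote ideation permitted (Section 7.4, criterion 19).

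**Enumeration.** Let L = lifetime yes, S = past-six-months yes, B = baseline-visit yes and P = post-dosing yes. S implies L, so (L, S) has 3 possible states, and there are 3 x 2 x 2 = 12 patterns. Compare two baselines:
- as written: L or S or B;
- recent only: S or B.

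Six patterns have P = yes:

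| L | S | B | As written | Recent only |
|---|---|---|---|---|
| no | no | no | no to yes | no to yes |
| no | no | yes | yes to yes | yes to yes |
| **yes** | **no** | **no** | **yes to yes** | **no to yes** |
| yes | no | yes | yes to yes | yes to yes |
| yes | yes | no | yes to yes | yes to yes |
| yes | yes | yes | yes to yes | yes to yes |

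Exactly one pattern changes: remote history only, then ideation on study. Among patterns with P = no, the same history is the only one affected. As written it reads yes-to-no, which looks like resolution of ideation that was not current. With a recent baseline it reads no-to-no.

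**Size, by assumption only.** Take subjects with no recent baseline ideation. Let p be the proportion of them with lifetime-only ideation, and k their on-study risk of ideation relative to the rest. The share of new-onset cases that the shift table does not show as a shift is

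share = pk / (pk + 1 - p).

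- k = 1: share = p. So p = 0.05 gives 5% and p = 0.15 gives 15%.
- k = 3, p = 0.05: 0.15 / (0.15 + 0.95) = 0.136, about 14%.
- k = 3, p = 0.15: 0.45 / (0.45 + 0.85) = 0.346, about 35%.

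If p is applied to a whole arm of 150, 5-15% is 150 x 0.05 = 7.5 to 150 x 0.15 = 22.5 subjects who could never appear as a new-onset shift. Neither p nor k is given in the documents.

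**The case against.** The strongest reply is that nothing is lost from the between-arm picture. The sentence that plans the shift analysis also plans the post-dosing distribution, which counts every subject with on-study ideation whatever the history, and Section 15.12 has suicidality results presented by study group. The listing covers grade 4-5 ideation and any behavior regardless of baseline status, and those grades are the ones the protocol itself uses for exclusion and referral. The DSMB reviews all safety data unblinded (Section 16.4.1). No test or decision rule rests on the shift table. All of this stands, and it limits the point to identifying new grade 1-3 ideation as new.

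A reader might infer that emergent cases are hidden from the report. The documents do not support that: the cases are counted by arm, and even in the shift table they appear in the yes-to-yes cell. A reader might also infer that people with a remote history are the ones most likely to develop ideation on study. The protocol gives no data on this, so any k above 1 is an assumption.

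For behavior the effect is close to empty. Criterion 19 removes lifetime attempts, including interrupted and aborted ones. That leaves mainly preparatory acts to set a remote behavior flag, and post-dose behavior is listed in any case.

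Finally, under Section 15.13 the SAP overrides the protocol. SAP version 2.0 is not among the documents available, and its addendum deals with the mITT set and does not mention the CSSRS. Version 2.0 may already define the baseline differently. This stands as a condition on the point.

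These replies do not remove the misclassification. The post-dosing distribution does not separate new from existing ideation, and the listing stops at grade 4. Under Section 15.9, new grade 1-3 ideation in a subject with remote history is nowhere identified as new.

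**Conclusion.** The point holds as a minor defect. Taken with the recall periods in Section 8.3.9, the rule in Section 15.9 classes one identifiable pattern wrongly, and always in the direction of fewer apparent new onsets. Section 15.9 does not itself use the word lifetime; the conclusion comes from reading the two sections together.

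The effect is confined to one descriptive safety table and, in practice, to ideation of grades 1-3. Its size cannot be computed from the documents. With equal risk it equals the prevalence of lifetime-only ideation, for example 5-15% of new-onset cases. With an assumed threefold risk it would be about 14-35%. These are shares of the new-onset labels in the shift table, not of cases missing from the report. The primary endpoint and the planned tests are not touched. If SAP version 2.0 already limits the baseline to recent answers, all that remains is to align Section 15.9 with it.

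**What to change.** In Section 15.9, and in SAP version 2.0 if it uses the same rule, define the ideation baseline for the shift analysis as a positive answer in the past-six-months part of the screening CSSRS or on the Since Last Visit CSSRS at the baseline visit. Report lifetime ideation by arm as a separate background row. The combined behavior-or-ideation class should take the same ideation baseline.

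Two further steps are optional: applying the same recall limit to the behavior baseline, and adding a count of subjects whose maximum ideation grade rises from baseline, since yes/no classes cannot show worsening.

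The cost is one changed derivation and one extra table row. No new data should be needed, because Section 8.3.9 says the screening form covers the past six months and criterion 19 already relies on answers for that period. Visits, eligibility and clinical handling are unaffected.
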